## 2. ■ 2. Definition of terms and abbreviations

Terms and abbreviations used in this analysis plan are defined as follows:

Terms and abbreviations	Definition
Patients who were followed up for 52 weeks (patients collected for the first volume)	Patients who started to receive this drug between August 16, 2014 and August 15, 2015.
Patients included at the 104th week of follow-up (patients collected for the first and second volume)	Patients who started to receive this drug between August 16, 2013 and August 15, 2014.
Patients included at the 156th week of follow-up (patients collected for the first, second, and third volume)	Patients who started to receive this drug by August 15, 2013.
Adverse events	Any unfavorable and unintended sign (including an abnormal laboratory finding), symptom, or disease, regardless of whether they are related to this drug or not
Adverse events that occurred during the period subject to safety analysis	
Adverse events that occurred from the start date of administration until the time as follows should be included.
 
 
Patients included at the 52th week of follow-up: The start date of administration of this drug + 392 days (56 weeks)
 
Patients included at the 104th week of follow-up: The start date of administration of this drug + 756 days (108 weeks)
 
Patients included at the 156th week of follow-up: The start date of administration of this drug + 1120 days (160 weeks)
 
Patients who discontinued to receive this drug: The last date of administration of this drug + 28 days
 

Adverse events that occurred in a period except for the period subject to safety analysis	
Adverse events that occurred before the start date of administration or after the following timing should be included
 
 
Patients included at the 52th week of follow-up: The start date of administration of this drug + 392 days (56 weeks)
 
Patients included at the 104th week of follow-up: The start date of administration of this drug + 756 days (108 weeks)
 
Patients included at the 156th week of follow-up: The start date of administration of this drug + 1120 days (160 weeks)
 
Patients who discontinued to receive this drug: The last date of administration of this drug + 28 days
 

Adverse reaction	Among adverse events, those for which causal relationship with this drug cannot be ruled out should be included

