The last date of the final treatment with this drug	
Of dates described in “Administration status of this drug” in survey sheet, records corresponding to following conditions should not be used for analysis.
 
Records of patients who started to receive this drug by August 15, 2013: The start date of the initial treatment with this drug + 1092 days < the start date
 
Records of patients who started to receive this drug between August 16, 2013 and August 15, 2014: The start date of the initial treatment with this drug + 728 days < the start date
 
Records of patients who started to receive this drug between August 16, 2014 and August 15, 2015: The start date of the initial treatment with this drug + 364 days < the start date
 
Of the last date of the treatment complemented by following [1] to [4], the latest date should be the last date of the final treatment with this drug.
 
[1] Data should be sorted by the start date of the treatment, separate volume, and the number of the cycle of treatment described in “Administration status of this drug” in that order.
 
[2] The start date of each data should be complemented at the last date of the initial and second treatment with this drug.
 
When a date is described in the section for the last date of the third or subsequent treatment, and there is no check mark in “Ongoing” box so that last date of the treatment can be

Name of data	Derivation and calculation method

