Test for tuberculosis	Test was implemented: If “test for tuberculosis or IGRA test” were implemented and “chest X-ray or CT scanning” was implemented. Tests were not implemented: Other than above situations
Test of hepatitis B	Test was implemented: If “HBV-DNA quantitative test” was implemented or patients are negative for “Hbs antigen test”, “Hbs antibody test”, and “Hbc antibody test”. Tests were not implemented: Other than above situations
Responding patients	Patients who were assessed to have obtained “improvement” and “significant improvement” as level of overall improvement are defined as responding patients.

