### 10.3. Efficacy analysis

Name of data	Derivation and calculation method
Level of overall improvement	Description of level of overall improvement in the survey sheet (assessment provided by attending physician) should be employed.
Clinical improvement	Patients with the level of improvement in endoscopy findings in the survey sheet of “2. shrinkage” or lower and comprehensive evaluation of gastrointestinal symptoms in the survey sheet of “1” or lower (0, 1) are assessed as patients with clinical improvement.
Complete remission	Patients with the level of improvement in endoscopy findings in the survey sheet of “1. remission or scar” and comprehensive evaluation of gastrointestinal symptoms in the survey sheet of “0” are assessed as patients with complete remission.
Improvement in gastrointestinal symptoms (abdominal pain, diarrhoea, other gastrointestinal symptoms)	If comprehensive evaluation of gastrointestinal symptoms or evaluation of each gastrointestinal symptom differs by 1 point or higher compared to those at the start of the administration of this drug (points of evaluation at the start of administration - those at each evaluation $\geq$ 1), patients are assessed as those who obtained improvement.

Name of data	Derivation and calculation method
Level of improvement in endoscopy findings	Description in “level of improvement in ulcer with the maximum diameter” in the level of endoscopy findings in the survey sheet should be employed.
Main symptoms and accessory symptoms of Behcet disease	Description in evaluations for each main and accessory symptom in efficacy evaluation in the survey sheet should be employed. “0” should be defined as “no symptom”, “1,2,3” should be defined as “there are any symptoms”, unknown or not described data should be defined as “unknown/not described”
CRP	Measurement in the survey sheet should be employed. If measurement is undetectable, the measurement should be deemed as undetectable limit.

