### 12.3. Time of evaluation of level of overall improvement

At the final follow-up: The evaluation at the last follow-up in which level of improvement for each patient was assessed as “1. significant improvement”, “2. improvement”, or “3. ineffective” is employed.

Patients who discontinued the administration of this drug should be followed-up until 14 days after the last date of the final administration of this drug, and within this period, the evaluation at the last follow-up in which level of improvement was assessed as “1. significant improvement”, “2. improvement”, or “3. ineffective” is employed.

In patients in whom follow-up was continued, the evaluation for following period should be included in analysis: Time Allowance at evaluation when the start date of the initial administration of this drug is defined as 1 is as follows:

Time of evaluation	Time Allowance(Day)
The last follow-up (patients who were continuously followed up)	

Patients who were followed up for 52 weeks: the start date of the initial administration of this drug + 37 (52 weeks + 14 days)

Time of evaluation	Time Allowance(Day)
	
 
Patients who were followed up for 104 weeks: the start date of the initial administration of this drug + 756 (104 weeks + 28 days)
 
Patients who were followed up for 156 weeks: the start date of the initial administration of this drug + 1120 (156 weeks + 28 days)
 

12.4. Time of evaluation of rate of clinical improvement, rate of complete remission, and level of improvement in endoscopy findings

Time Allowance at evaluation when the start date of the initial administration of this drug is defined as 1 is as follows:

Time of evaluation	Time Allowance(Day)
Within 24 weeks after the administration start	1-168
At least 24 weeks and within 52 weeks after the administration start	169-364
At least 52 weeks and within 76 weeks after the administration start	365-532
At least 76 weeks and within 104 weeks after the administration start	533-728
At least 104 weeks and within 128 weeks after the administration start	729-896
At least 128 weeks and within 160 weeks after the administration start	897-1121

Data of rate of clinical improvement and complete remission with evaluation of endoscopy findings obtained within Time allowance and evaluation of gastrointestinal symptoms within 4 weeks before and after the date of endoscopy implementation should be employed.

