**“2.19.1 Treatment for patients who showed insufficient response to treatment”**

Patients included in analysis: In patients included in safety analysis, patients who discontinued the survey because of “insufficient effect” or patients in whom dose or the number of administration was adjusted because of “insufficient effect” should be

included.

Objective of analysis: Presence or absence of drugs used after discontinuation of this drug and distribution of the drugs used after discontinuation of this drug are shown.

Analysis items: The number of patients included in analysis should be calculated.

The number of patients and rate of these patients by “drugs used after discontinuation of this drug” and ”detailed classifications of drug used after the discontinuation of this drug“ defined in “11 method of dividing hierarchy for data” should be calculated.

Date of patients in whom dose or the number of administration was adjusted because of “insufficient effect” should be obtained from “[HUMIRA BD] converted data for provision for analysis”.

Notes: Detailed classifications of drug used after the discontinuation of this drug may be overlapped.

“2.19.2 Dosage and administration for patients who showed insufficient response to treatment”

Patients included in analysis: In patients included in safety analysis, patients who discontinued the survey because of “insufficient effect” or patients in whom dose or the number of administration was adjusted because of “insufficient effect” should be included.

Objective of analysis: Distribution of dosage and administration for patients who showed insufficient response to treatment is shown.

Analysis items: The number of patients included in analysis should be calculated.

The number of patients and rate of these patients to those included in analysis should be calculated by presence or absence of discontinuation and classification of dosage and administration (patients discontinued by the initial or second administration, patients who received this drug 3 times or more, the maximum dose for the third or subsequent administration is 40 mg/2 weeks, 40 mg/1 week, 80 mg/2 weeks, 80 mg/1 week, 160 mg/2 weeks, 160 mg/1 week, and others). Items with the number of 0, output by items should not be made.

Date of patients in whom dose or the number of administration was adjusted because of “insufficient effect” should be obtained from “[HUMIRA BD] converted data for provision for analysis”.

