#### “3.4 Aggregation of efficacy by patient characteristics”

Patients included in analysis: Patients included in efficacy analysis

Objective of analysis: As primary survey item, efficacy ratio in level of improvement at the last follow-up for factor analysis.

Analysis items: The number of patients included, the number of responding patients regarding level of overall improvement (significant improvement and improvement) and rate of these patients to those included in analysis, the number of patients who showed ineffectiveness in level of overall improvement and rate of these patients to those included in analysis, and test provided for effectiveness (Fisher’s exact test for nominal scale factors, and Mann-Whitney u test for ordinal scale factors) were calculated by following patient characteristics.

Notes: Patient characteristics are as follows:

Age (years), sex, disease duration (years), complication, hepatic function disorder as complication, renal impairment as complication, medical history, allergy history, smoking habit, self-administration as administration status of this drug, previously used drug/previous treatment, biological preparation adalimumab as previously used drug, biological preparation infliximab as previously used drug, steroid as previously used drug, immunomodulative drug as previously used drug, immunosuppressive drug as

previously used drug, oral adrenocortical steroid as concomitant drug, oral mucosa recurrent aphthous ulcer as main symptoms of Behcet disease other than gastrointestinal symptoms, cutaneous symptoms as main symptoms of Behcet disease other than gastrointestinal symptoms, eye symptoms as main symptoms of Behcet disease other than gastrointestinal symptoms, ulcer of vulva as main symptoms of Behcet disease other than gastrointestinal symptoms, arthritis without deformity or rigidity as accessory symptoms of Behcet disease other than gastrointestinal symptoms, epididymitis as accessory symptoms of Behcet disease other than gastrointestinal symptoms, vascular lesion as accessory symptoms of Behcet disease other than gastrointestinal symptoms, moderate or higher degree central nervous lesion as accessory symptoms of Behcet disease other than gastrointestinal symptoms, diagnostic classification of Behcet disease, days until the last date of the administration, and mean daily dose.

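### SAP sections 12.3 and 10.1 allow a patient recorded as stopping for insufficient effect to count as a responder in Tables 3.1 and 3.4 on an earlier rating

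*SAP*

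**What the plan says.** The outcome is the attending physician's rating, taken as recorded. Section 10.3 says: "Description of level of overall improvement in the survey sheet (assessment provided by attending physician) should be employed".

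Section 12.3 decides which rating is used. Patients who discontinued "should be followed-up until 14 days after the last date of the final administration of this drug", and the rating used is, "within this period, the evaluation at the last follow-up in which level of improvement was assessed as" significant improvement, improvement or ineffective. The section gives the end of the period. It gives no start and no maximum age for the rating.

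Section 10.1 then classifies the patient: those with improvement or significant improvement "as level of overall improvement are defined as responding patients". It sets no condition on whether or why the patient stopped.

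Section 11 lists insufficient effect as a separate reason for discontinuation. That reason is used in Tables 2.19.1 and 2.19.2, both on the safety set; the first is titled "Treatment for patients who showed insufficient response to treatment". Table 3.1 reports overall improvement at last follow-up under 12.3. Table 3.4 states its objective as: "As primary survey item, efficacy ratio in level of improvement at the last follow-up for factor analysis".

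**The concern.** Two recorded facts about one patient can disagree: a stop for lack of effect, and a last usable rating of improvement. The plan settles the disagreement silently in favour of the rating, even if that rating was made well before the stop.

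The responder ratio is the outcome of Table 3.1 and of the factor analysis in Table 3.4, and factors that may contribute to efficacy are one of the survey's objectives in section 4.1. A treatment failure counted as a responder raises the reported ratio and blurs the comparisons between patient characteristics. The published tables would not show how many such patients there are.

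**Working it through.** The plan states no response rate, discontinuation rate or sample size that bears on this, so there is no figure to reproduce. The check traces the rule, then its dates, then its possible size.

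**1. Does anything link the reason for stopping to responder status?**
- Section 8 excludes from the efficacy set only non-target disease and patients whose efficacy cannot be assessed. A stop for lack of effect is neither.
- Section 9.1 leaves missing data unfilled unless an item says otherwise, so there is no general non-responder rule.
- Sections 10.1, 10.3 and 12.3 and Tables 3.1 and 3.4 do not mention the reason for stopping.
- Tables 2.19.1 and 2.19.2 describe later drugs and dosage only.

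No link exists.

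**2. How old can the rating be if the period has no start?** Section 10.1 treats a patient as discontinued if the last date is earlier than start + 350, 700 or 1064 days (52-, 104- and 156-week cohorts).
- Latest possible last date: start + 349, 699 or 1063.
- Period closes 14 days later: start + 363, 713 or 1077.
- Suppose the only usable rating was made 28 days after start (an assumption). Its age at closure is 363 − 28 = 335, 713 − 28 = 685 or 1077 − 28 = 1049 days. It would still be used.

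**3. Does the 14-day limit remove the stop visit?** For doses 1 and 2, section 10.1 sets the last date to the injection day: "The start date of each data should be complemented at the last date of the initial and second treatment with this drug".
- Doses on days 1 and 15: limit 15 + 14 = day 29.
- Last date on day 155: limit 155 + 14 = day 169.

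Days 29 and 169 are the nominal week-4 and week-24 record dates in section 12.5. A visit exactly 14 days after the last date is kept; a later one is lost. Item (19) of Table 2.3 provides for a rating that is on the survey sheet but not obtained under 12.3, so the plan expects some ratings to fall outside.

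**4. Size.** Let d be the share of the efficacy set who stopped with insufficient effect ticked, and f the share of those whose last usable rating is favourable. With the denominator fixed, counting them all as ineffective lowers the responder rate by d × f. Both inputs are assumptions.

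| d | f | Change in responder rate |
|---|---|---|
| 5% | 25% | 1.25 points |
| 10% | 50% | 5 points |
| 20% | 75% | 15 points |

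This is the gap between two ways of classifying these patients. It does not measure how many ratings the 14-day limit discards.

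**The case against.** The endpoint is the physician's judgement. Overriding it with a tick-box creates a different endpoint, in an uncontrolled survey with no confirmatory efficacy test. This stands, and is why the physician's rating should remain the main result.

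The phrase about the period could also mean only the 14 days after the last dose. On that reading an old rating could not be carried forward. The open start is the more natural reading, because the text runs up to a limit and picks the latest of several evaluations. Even on the narrow reading, a patient who stopped for insufficient effect and was rated improved in those 14 days is a responder.

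A reader might infer three stronger points, which the document does not support:

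- **That the 14-day limit systematically drops ineffective ratings made at the stop visit and so biases the rate upward.** Visits need not follow doses, since self-administration is part of the survey, and a visit at exactly 14 days is kept. The limit also drops favourable ratings made later, possibly on replacement treatment. Applying it to the section 12.5 windows cuts 13 of 28 days at week 4 and 14 of 29 at week 24, but those windows govern gastrointestinal symptom scores. The SAP gives no rating schedule for overall improvement, so the net direction of this loss is unknown.
- **That the limit should be 28 days because safety uses "The last date of administration of this drug + 28 days".** That is an adverse-event window. A 14-day on-treatment limit for efficacy is defensible.
- **That appearing in both Tables 2.19.1/2.19.2 and the responder count is a contradiction.** Those tables also include patients whose dose or number of administrations was adjusted for insufficient effect, and such a patient may respond later. The difficulty concerns those who discontinued.

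**Conclusion.** The point holds in a limited form. Under 12.3 and 10.1 as written, a patient recorded as stopping for insufficient effect can be counted as a responder in Tables 3.1 and 3.4, and nothing in those tables would reveal it. That follows from the text without assumptions. That the deciding rating may be very old depends on reading the period as having no start.

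How often this happens is unknown. The range of 1.25 to 15 points rests wholly on the assumed shares and should not be read as an estimate of bias. The gap warrants an inexpensive addition to the plan. It does not warrant replacing the endpoint or moving the 14-day limit.

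**What to change.** Keep the physician's rating under 12.3 as the main result. Then:

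1. Pre-specify in section 12.3 and in Tables 3.1 and 3.4 an additional row in which every patient who discontinued with insufficient effect ticked counts as ineffective, whether it is the only reason or one of several.
2. Report how many discontinued patients had a rating discarded because it fell more than 14 days after the last dose, and what each discarded rating was. This would show whether the limit matters and in which direction.

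The added row needs one derived flag, built from a reason for discontinuation that the survey sheet already records. The count of discarded ratings needs the rating dates that 12.3 already relies on. The downside is a somewhat lower responder rate in the added row, which should be labelled as a sensitivity result.

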Patients who discontinued the administration	If the last date of the final administration of this drug corresponds to following conditions, the patients are deemed to be those who discontinued the administration.

Name of data	Derivation and calculation method
	
Patients who started to receive this drug by August 15, 2013: The start date of the initial administration + less than 1064 days
 
Patients who started to receive this drug between August 16, 2013 and August 15, 2014: The start date of the initial administration + less than 700 days
 
Patients who started to receive this drug between August 16, 2014 and August 15, 2015: The start date of the initial administration + less than 350 days

Presence or absence of reasons for discontinuation	
If patients correspond to those who discontinued the administration and there is at least one check mark in any “Reasons for discontinuation” boxes in “Discontinuation of the survey” section in the survey sheet, the patients are deemed as having reasons for discontinuation and if no description is found in the “Reasons for discontinuation” box in the survey sheet of patients defined as those who discontinued the administration, such patients are defined as patients whose reason for discontinuation is “unknown or not described reason”.

Patients who continue to participate in the survey	
Patients who do not correspond to those who discontinued administration are deemed as patients who continue to participate in the survey.

Presence or absence of complications	
If there is a check mark in a box for complication in “patient information” in survey sheet, such patients are deemed to have complication, and if a column for “presence or absence of complications” is not completed and cannot be assessed, whether patients have complication or not is deemed as unknown or not described, and in any other situations, patients are deemed to have no complication.

Presence or absence of medical history	
If there is a check mark in a box for medical history in “patient information” in the survey sheet, patients deemed to have medical history, and a column for “presence or absence of medical history” is not completed and cannot be assessed, whether patients have medical history or not is deemed as unknown or not described, and in any other situations, patients are deemed to have no medical history.

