12.5. Time of evaluation of gastrointestinal symptoms

Time Allowance at evaluation when the start date of the initial administration of this drug is defined as 1 is as follows:

Time of evaluation	Time Allowance(Day)
Administration start	until 1 (record date is day 1)
4 weeks after the administration start	15-42 (record date is day 29)
8 weeks after the administration start	43-70 (record date is day 57)
12 weeks after the administration start	71-98 (record date if day 85)
24 weeks after the administration start	155-183 (record date if day 169)

Time of evaluation	Time Allowance(Day)
52 weeks after the administration start	351-379 (record date is day 365)
76 weeks after the administration start	505-561 (record date is day 533)
104 weeks after the administration start	701-757 (record date is day 729)
128 weeks after the administration start	869-925 (record date is day 897)
156 weeks after the administration start	1065-1121 (record date is day 1093)

The latest data of that obtained within Time allowance should be included in analysis and if there is multiple data for the same day, data with the worse value (in the order of 4,3,2,1,0) should be included in analysis.

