#### 12.6. Time of evaluation of main and accessory symptoms of Bechet disease

Time Allowance at evaluation when the start date of the initial administration of this drug is defined as 1 is as follows:

Time of evaluation	Time Allowance(Day)
Administration start	until 1 (record date is day 1)
52 weeks after the administration start	351-379 (record date is day 365)
104 weeks after the administration start	701-757 (record date is day 729)
156 weeks after the administration start	1065-1121 (record date is day 1093)

The data on the closest day to the record date should be included in analysis and if there is multiple data for the same day, data with the worse value should be included in analysis.

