Notes: Level of overall improvement to be output should be according to “12.3 Time of evaluation of overall improvement”.

In addition, level was defined as “Significant improvement”, “improvement,” “ineffective”, or “efficacy could not be assessed”.

For adverse events that occurred outside the period subject to safety analysis, retrieving flag should be displayed as 1 (applicable) or 2 (not applicable).

Retrieving flag for complete type Behcet disease, incomplete type Behcet disease, and suspected Behcet disease, 10.1 diagnostic classifications of Behcet disease should be referred to.

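### SAP 12.3 cuts off the overall-improvement rating of continuing 52-week patients at start + 37 days, although its own gloss (52 weeks + 14 days) is 378 days

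*SAP*

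**What the plan says.** Section 12.3 defines the final overall-improvement rating as the last assessable one within a permitted period. For patients who stopped the drug, that period ends 14 days after the last administration. For patients who continued, it ends a fixed number of days after the first administration, depending on the cohort:

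- 52-week cohort: "the start date of the initial administration of this drug + 37 (52 weeks + 14 days"
- 104-week cohort: "the start date of the initial administration of this drug + 756 (104 weeks + 28 days"
- 156-week cohort: "the start date of the initial administration of this drug + 1120 (156 weeks + 28 days"

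The rating so selected is used in several places. Section 10.1 builds the responder definition on it: patients rated as improved or significantly improved "as level of overall improvement are defined as responding patients". Table 3.1 reports the rating at last follow-up, and Table 3.4 tests responder status against patient characteristics. For list 1.4 the note in section 13.1 states: "Level of overall improvement to be output should be according to" section 12.3. Lists 1.16 and 2.3 (item 19) rely on the same rule.

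**The concern.** The day count and the gloss on the 52-week line cannot both be right. A limit of 37 days is a little over five weeks after the first administration, yet it is meant to close a one-year follow-up.

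Taken literally, the rule also works backwards within 12.3. A patient who stopped at start + 300 could contribute a rating up to start + 314, while a patient who completed the year could contribute nothing after start + 37. The year-end ratings of the completers would be replaced by very early ratings, or by none.

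The stake is the overall efficacy result of the survey (Table 3.1) and the factor analysis of response (Table 3.4), for one of the three cohorts.

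**Working it through.** **Inputs.** The three limits and glosses come from 12.3, the visit windows from 12.5 to 12.7 and the discontinuation thresholds from 10.1.

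**Step 1: limit against gloss.** Offset = weeks × 7 + allowance in days.

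| Cohort | Gloss | Computed | Printed |
|---|---|---|---|
| 52 weeks | 52 × 7 + 14 | 378 | 37 |
| 104 weeks | 104 × 7 + 28 | 756 | 756 |
| 156 weeks | 156 × 7 + 28 | 1120 | 1120 |

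Two of the three lines reproduce exactly and the 52-week line does not. No other counting gives 37: 52 weeks alone is 364, counting one day either side gives 377 or 379, and 52 weeks + 28 days is 392. The figure 392 does appear in section 2, as the end of the adverse-event period for this cohort, but it does not fit a 14-day allowance.

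**Step 2: agreement with the visit windows.** The SAP counts the start date as day 1, so start + n is day n + 1.

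- Start + 378 = day 379. The 52-week window in 12.5, 12.6 and 12.7 is "351-379 (record date is day 365", ending on day 379.
- Start + 756 = day 757 and start + 1120 = day 1121, the ends of the 104- and 156-week windows.

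With 378, all three cohorts follow one convention.

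**Step 3: agreement with the discontinuation rule.** For the 52-week cohort, 10.1 counts a patient as discontinued if the last administration date is "The start date of the initial administration + less than 350 days". The three thresholds are

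- 364 − 14 = 350
- 728 − 28 = 700
- 1092 − 28 = 1064

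These are the same tolerances as in 12.3, taken on the other side of the nominal date: 14 days for the 52-week cohort and 28 days for the other two.

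**Step 4: size of the error.**

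- Printed limit against gloss: 378 − 37 = 341 days too early.
- Printed limit against the earliest last administration date of a continuing 52-week patient: 350 − 37 = 313 days before it.
- In weeks: 37 / 7 = 5.3, against 378 / 7 = 54.
- As a yardstick only, against the gastrointestinal-symptom windows of 12.5: start + 37 is day 38. The 4-week window is "15-42 (record date is day 29", which has 28 days, and days 15 to 38 are 24 of them. The 8-, 12-, 24- and 52-week windows begin on days 43, 71, 155 and 351, so none of their days is admitted.

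**The case against.** The strongest reply is that the line corrects itself. The intended interval stands beside the wrong figure, the two neighbouring lines show the pattern, and a programmer would have to overlook all of this to code 37. On that view it is a misprint. This stands as a limit on the likelihood of harm. It does not remove the point, because the figure is an operative cut-off for an efficacy result and the SAP leaves two contradictory values for it.

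A digit may have been lost when the PDF was read. That cannot be ruled out, although the rest of the line is intact. A look at the source page settles it.

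Three supporting points need qualification:

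- Sections 12.5 to 12.7 and 10.1 do not govern the overall-improvement rating. They agree with 378, but the gloss is what establishes it.
- The 350-day threshold applies to the derived last administration date, which 10.1 allows to be imputed, for example when treatment is marked as ongoing. The 313-day gap therefore holds for that derived date and not necessarily for an observed dose. It also takes the continuing patients of 12.3 to be those whom 10.1 does not class as discontinued. That is the natural reading, but 12.3 does not state it.
- What happens to a patient left without a rating is only partly specified. List 2.3, item 19, outputs such a patient as unknown when the survey sheet does hold a rating, and 9.2 keeps unknowns in rate denominators but drops them from tests. Carrying this into Tables 3.1 and 3.4 is an inference: section 11 gives the rating only three levels, and section 8 excludes patients whose efficacy cannot be assessed. By any of these routes the late ratings are lost.

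**Conclusion.** The concern holds. The 52-week limit in 12.3 is wrong by its own gloss: 37 is printed where 378 follows, a shortfall of 341 days. The conclusion rests on the gloss and on simple arithmetic; the agreement with the visit windows and the discontinuation thresholds is corroboration.

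The effect is confined to continuing patients of one cohort out of three, and arises only if the printed number is coded literally. The SAP gives neither patient counts nor a schedule for the overall-improvement ratings, so neither the share of patients affected nor the change in the response rate can be stated. It should be corrected because the main efficacy tables depend on this cut-off. It is not evidence of a flaw in the design.

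**What to change.** Check the line in 12.3 against the source page. If 37 is printed there, replace + 37 by + 378, so that the limit equals its gloss and coincides with day 379 in 12.5 to 12.7. Leave the 104- and 156-week limits as they are. If programs for Tables 3.1 and 3.4 or lists 1.4, 1.16 and 2.3 already exist, confirm that they use 378.

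The cost is one figure in the SAP. No new data are needed and no other section changes.
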